1 OBJECTIVES

1.1 Primary Objectives

- 1.1.1 To estimate the 1-year disease stabilization rate associated with the use of PEGINTERFERON ALFA-2B in patients with progressive unresectable or recurrent craniopharyngiomas following surgery alone who have not received radiation therapy.
- 1.1.2 To estimate the sustained objective response rate (PR+CR) to PEGINTERFERON ALFA-2B in patients with craniopharyngiomas which progress or recur following radiation therapy.

1.2 Secondary Objectives

- 1.2.1 To estimate the response rate in patients with progressive unresectable or recurrent craniopharyngioma treated with PEGINTERFERON ALFA-2B by study stratum.
- 1.2.2 To estimate the progression-free survival distribution for patients with unresectable or recurrent craniopharyngiomas treated with PEGINTERFERON ALFA-2B by study stratum.
- 1.2.3 To evaluate the toxicity profile of PEGINTERFERON ALFA-2B in children with unresectable or recurrent craniopharyngiomas.
- 1.2.4 To compare the protocol specific disease assessment criteria to MacDonald criteria during the first year of treatment in stratum I and also at the time of objective response and progressive disease in both strata.
- 1.2.5 To characterize evidence of WNT and MAPK pathway activation in resected tumor tissue in patients with craniopharyngiomas by immunohistochemistry and pyrosequencing and correlate these results with outcome and response data.

2 BACKGROUND

2.1 Study Disease(s)

Craniopharyngiomas account for approximately 4% of brain tumors in patients younger than 15 years of age. They are believed to arise from embryonic squamous cell rests along the hypophyseal-pharyngeal duct. Complete surgical resection is often not possible without significant morbidity because of the tumor's proximity to the optic chiasm, third cranial nerve, hypothalamus and internal carotid arteries and branches. Despite complete resection, recurrence rates range from 20% to as high as 50%. Subtotal resection followed by radiation therapy achieves at least comparable results in terms of recurrence rates and survival. Therefore, either complete resection or subtotal resection followed by radiation therapy is considered standard of care for patients with newly diagnosed craniopharyngiomas.

Unfortunately, permanent deleterious effects on behavior, learning and endocrine function following surgery and/or radiation therapy are common in children with craniopharyngioma and can be devastating. Multiple endocrinopathies are almost universal, but the effects of hypothalamic damage including hypothalamic obesity and impaired socialization and poor

academic performance ("hypothalamic syndrome") are often not remediable. The effects of radiation are relatively age dependent, with more significant damage occurring in younger children. An effective medical therapy that can defer the need for radiation therapy, particularly for young children, or salvage those tumors that have recurred following radiation therapy would be of tremendous benefit both in terms of overall survival as well as quality of life.

2.2 SYLATRON (Peginterferon alpha-2b)

2.2.1 Rationale for alpha-interferon

The interferons are a family of naturally occurring, small proteins produced and secreted by virtually all eukaryotic cells in response to viral infections or to various biologic and synthetic inducers. Interferons exert antitumor activity through direct antiproliferative and cytotoxic effects as well as modulation of the host immune response.¹¹ Interferon is also a potent inhibitor of angiogenesis as evidenced by its utility in the treatment of life-threatening hemangiomas of infancy.¹²

Craniopharyngiomas and squamous cell skin carcinoma are believed to have the same embryologic origin. Squamous epithelium, usually with some evidence of keratinization, is characteristically found in both the cystic lining and the solid component of craniopharyngiomas.² When administered both intralesionally and systemically, interferon alpha has significant activity against squamous cell skin carcinoma. Intralesional injections of alpha interferon for 3 weeks resulted in histologically proven eradication of squamous cell carcinoma in 33 out of 34 patients.¹³ Treatment with subcutaneous alpha-2a interferon (3 million IU/d) and oral cis-retinoic acid for two months in patients with advanced squamous cell carcinoma resulted in an overall response rate of 68%, and a 93% response rate for those with localized disease.¹⁴

Based on this, a Phase II study of alpha-interferon was performed in pediatric patients with progressive or recurrent craniopharyngiomas. 15 Interferon alpha-2a was administered subcutaneously daily for 16 weeks followed by a 32 week maintenance phase where the interferon was given three times/week. Three of 12 evaluable patients showed a minor response (n=1), partial response (n=1) or complete response (n=1); the patient with the PR also showed improvement in visual fields. The median time to progression was 25 months (range 3-37+ months with 3 patients without progression as of last follow-up). The cystic component of the tumor often increased temporarily during the first several months of treatment. Toxicities requiring temporary discontinuation and/or dose reduction were common during the initial 16 weeks of therapy. All patients developed fever shortly after receiving the first dose of IFN, usually accompanied by chills and myalgias. Two patients with panhypopituitarism developed hypotension and lethargy during the fever, requiring stress dose steroids. discontinuation and/or dose reduction was required for toxicity in nine (60%) of the 15 patients during the first 8 weeks of treatment but resolved after temporary discontinuation and/or dose reduction. These toxicities included worsening seizures, transaminase elevations, rash and anorexia/weight loss.

Intralesional interferon-alpha has also shown efficacy against craniopharyngiomas. In a multicenter study, 60 patients with predominantly cystic craniopharyngiomas were treated with every other day intra-cystic interferon-alpha. Forty-seven (78%) of the 60 patients had a > 50%

decrease in the size of the cyst.¹⁶ A separate study of 8 patients with cystic craniopharyngiomas treated with intra-cystic alpha-interferon showed an increase in the apoptotic factor soluble FasL concentrations in the cyst fluid of all 8 patients as the cyst decreased in size in response to treatment, suggesting that interferon works by inducing Fas-mediated apoptosis.¹⁷

2.2.2 Rationale for Pegylated Interferon (PEGINTERFERON ALFA-2B)

In tumor cell lines, continuous and prolonged exposure to interferon optimizes both the anti-proliferative and anti-angiogenic effect¹⁸⁻²¹ and the highest response rates in patients with metastatic melanoma have been obtained with uninterrupted schedules.¹⁸ When interferon was removed from the medium, glioma cell line growth rapidly returned to the pretreatment rate.²⁰

Conjugating proteins with poly-ethylene-glycol (PEG) almost invariably lengthens the plasma half-life by reducing sensitivity to proteolysis, thereby increasing the area under the curve (AUC) and providing protracted activity.²² Pegylation of interferon enhances the therapeutic ratio in patients with hepatitis C, and was more effective than a regimen of non-pegylated interferon given 3 times/week.²³ PegIntron has received FDA approval for this indication at a dose of 1 mcg/kg/dose/week when given as a single agent.

2.2.3 Rationale for PEGINTERFERON ALFA-2B Dose

Although interferon-alpha has been used to treat a variety of neoplasms, the optimal dose in oncology has not been established. In vivo studies have not shown a clear dose-response relationship in solid tumors, other than possibly for melanoma²⁴. In CML, low dose interferon is just as effective as higher doses²⁵ whereas toxicity is clearly dose-related.

A Phase I study of PegIntron alpha-2b in pediatric patients with neurofibromatosis-related plexiform neurofibromas has recently been published.²⁶ The recommended Phase 2 dose (RP2D) was 1 mcg/kg/week with fatigue and intolerable behavioral toxicities seen at higher doses. There was only one DLT (myoclonus) in 12 patients treated at the RP2D. This toxicity had not been seen previously and was felt to be possibly related, although it continued intermittently even after the drug was discontinued. Only 1 other patient required a dose reduction for grade 3 elevation of transaminases. This dose is also the FDA approved dose for the treatment of hepatitis C in adults when used as monotherapy. Although a higher dose of PEGINTERFERON ALFA-2B is used in adult patients with melanoma, where there is a known dose-response curve, a dose of 1 mcg/kg/week resulted in a prolonged CR in one of the patients in the pilot study.²⁷

Many, if not most patients with craniopharyngiomas have panhypopituitarism and require stress doses of steroids to remain hemodynamically stable in the face of high fever and/or chills, which are common dose-related side effects of interferon, and almost universally seen with higher doses, particularly with short acting interferon. A dose of 1 mcg/kg/week has been found to be well tolerated in pediatric patients²⁶, causing only mild to moderate constitutional symptoms which subside over time, and has shown efficacy in the pilot study at Children's Hospital of Pittsburgh.²⁷ Therefore, a dose of 1 mcg/kg/week will be utilized for all patients in this protocol, regardless of age.

2.3 Pediatric Clinical Trials

[figure not shown]
As stated in Section 2.2.1, a Phase II study of alpha-interferon was performed in pediatric patients with progressive or recurrent craniopharyngiomas.¹⁵ Interferon alpha-2a was administered subcutaneously daily for 16 weeks followed by a 32 week maintenance phase with the interferon given three times/week. Three of 12 evaluable patients had an objective response and one patient also showed improvement in visual fields: the median time to progression was 25 months.

2.4 Rationale for Changing Study Drug PegIntron to SYLATRON

Merck has decided to voluntarily discontinue the manufacture of the PegIntron vials, Injection, for subcutaneous use, for distribution in the United States for business reasons. The decision is not based on any safety or efficacy findings with this product. This decision is due to scientific advancement, changes in treatment practices, and the consequent reduction in the demand for PegIntron. SYLATRON, which has the same active ingredient as PegIntron (Peginterferon alfa-2b) with different Dosage Strength, is proposed to replace PegIntron as the study drug of PBTC-039.

2.5 Rationale for Correlative Studies

2.5.1 WNT and MAPK pathway activation

Recent genomic studies have demonstrated that each of the two histologic subtypes of craniopharyngioma (adamantinomatous and papillary) is characterized by the presence of a specific genetic alteration.²⁸ Adamantinomatous craniopharyngiomas, which are most common in children, exhibit near-universal mutation of beta-catenin (*CTNNB1*), confirming recent evidence that craniopharyngiomas arise from activation of beta-catenin (a Wnt pathway gene) in pituitary progenitors during embryogenesis²⁹. Of note, craniopharyngiomas with mutations in *CTNNB1* can be reliably identified by detection of nuclear immunoreactivity for the beta-catenin protein, which is the most commonly-used clinical test for alterations in this gene. These results confirmed an earlier study where all 10 cases of adamantinomatous craniopharyngioma harbored beta-catenin mutations and stained for nuclear expression of beta-catenin.³⁰ Papillary

craniopharyngiomas, in contrast, are characterized by frequent *BRAF* V600E mutations, indicating activation of the MAPK signaling pathway.²⁸ Although in general mutations in *CTNNB1* and *BRAF* are mutually-exclusive in craniopharyngiomas, cases have been identified in which both genes are mutated in the same tumor.³¹ We propose to validate these observations using immunohistochemistry for nuclear beta-catenin and pyrosequencing for detection of *BRAF* V600E in FFPE sections in this pediatric series of craniopharyngiomas.

2.5.2 MRI Study

Standard high resolution MR imaging dedicated to the suprasellar/sellar region with gadolinium has been used in previous studies of interferon in patients with recurrent craniopharyngioma. Volumetric analyses of tumor size have been reported to more accurately detect change in tumor volume than the diameter method. 32

The product of the greatest perpendicular linear diameters will be compared to central volumetric analysis of the cystic and solid component of the tumor and compared to assessment of disease response.

3 PATIENT SELECTION

3.1 Eligibility Criteria

All subjects must meet the following inclusion and exclusion criteria. No exceptions will be given. Imaging studies to establish eligibility must be done within three (3) weeks prior to registration and 4 weeks of starting therapy. All subjects must have baseline MRI scans of the brain with thin cuts through the sella (see Section 9.3).

All other evaluations necessary to establish eligibility for study entry must be done within two (2) weeks prior to registration.

3.1.1 Tumor

Patient must have a histologically verified diagnosis of craniopharyngioma.

Stratum 1: Patients with progressive unresectable or recurrent craniopharyngiomas treated with surgery alone, who have not received radiation therapy. Patients with unresectable craniopharyngiomas, (i.e. residual measurable disease following surgical resection) will be enrolled at the time of progression.

Stratum 2: Patients with progressive or recurrent craniopharyngiomas following radiation therapy. The patient must be at least 6 months post-irradiation to be eligible.

3.1.2 Disease Status

All patients must have measurable residual disease defined as tumor measurable in two perpendicular diameters on MRI. Measurements are required for both the solid and cystic components

3.1.3 Prior Therapy

Subjects must have recovered from the acute toxicities of all prior therapy before entering this

study. For those acute baseline adverse events attributable to prior therapy, recovery is defined as a toxicity Grade \leq 2, using CTCAE v.4.0, unless otherwise specified in the Inclusion and Exclusion Criteria.

3.1.4 Myelosuppressive chemotherapy:

Subjects must have received their last dose of known myelosuppressive anticancer chemotherapy at least three (3) weeks prior to study registration or at least six (6) weeks if nitrosourea.

3.1.5 Investigational / Biologic agent:

Subjects must have received their last dose of investigational or biologic agent ≥ 7 days prior to study registration.

- In the event that a subject has received an investigational or biologic agent and has experienced ≥ Grade 2 myelosuppression, then at least three (3) weeks must have elapsed prior to registration.
- If the investigational or biologic agent has a prolonged half-life (≥ 7 days) then at least three (3) weeks must have elapsed prior to registration.

3.1.6 Monoclonal antibody treatment:

Subjects must have completed at least 3 half-life periods from the last dose of monoclonal antibody prior to registration.

Note: A list of half-lives of commonly used monoclonal antibodies is available on the PBTC website under Generic Forms and Templates

3.1.7 Radiation

Stratum 1: Patients must not have received radiation therapy.

Stratum 2: Patients must have received radiation therapy, which may include gamma knife or P32:

- More than 6 months from the time of enrollment if the recurrence is predominantly solid
- More than 12 months from the time of enrollment if the recurrence is predominantly cystic

3.1.8 Growth factors:

At least 7 days since the completion of therapy with a hematopoietic growth agent (filgrastim, sargramostim, and erythropoietin) and 14 days for long-acting formulations.

3.1.9 Performance Status

Karnofsky Performance Scale (KPS for \geq 16 yrs of age) or Lansky Performance Score (LPS for < 16 years of age) \geq 60 assessed within two weeks prior to registration (See Appendix A)

3.1.10 **Age:**

18 months – 25 years (Minimum weight 20 Kilogram is required to be eligible for the study, since the minimum injection volume of SYLATRON is 0.05 ml, 20 mcg, SQ as suggested by Merck)

3.1.11 Organ Function:

Patients must have evidence of normal organ function as defined by:

- ANC≥ 1000/µl (unsupported)
- Platelets $\geq 100,000/\mu l$ (unsupported)
- Hg \ge 8g/dL (unsupported)
- ALT \leq 2.5 x the upper limit of institutional normal
- Total bilirubin $\leq x$ 1.5 upper limit of institutional normal
- Serum creatinine ≤ 1.5 x the upper limit of normal for age, or calculated creatinine clearance or nuclear GFR ≥ 70 ml/min/1.73 m²

Table 1

| Serum Creatinine for Age/Gender | | | | |
|---------------------------------|-------------------------------------|--------|--|--|
| Age | Maximum Serum Creatinine (mg/dL) | | | |
| | Male | Female | | |
| 1 to < 2 years | 0.6 | 0.6 | | |
| 2 to < 6 years | 0.8 | 0.8 | | |
| 6 to < 10 years | 1 | 1 | | |
| 10 to < 13 years | 1.2 | 1.2 | | |
| 13 to < 16 years | 1.5 | 1.4 | | |
| ≥ 16 years | 1.7 | 1.4 | | |

The threshold creatinine values in this Table were derived from the Schwartz formula for estimating GFR (Schwartz et al. J. Peds, 106:522, 1985) utilizing child length and stature data published by the CDC.

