6 DOSING DELAYS/DOSE MODIFICATIONS

If patients drop below 20 kg during SYLATRON treatment, they can have SYLATRON held for up to 3 weeks for increasing nutrition. If they can gain weight and return to \geq 20 kg, they could restart SYLATRON and not make up lost weeks. This could happen twice before being removed from study.

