6.1 Constitutional Symptoms

Every attempt should be made not to stop the drug for constitutional symptoms during the first three weeks, since these symptoms usually improve. Patients with persistent (i.e. lasting > 48 hours) grade 2 or higher constitutional symptoms occurring after the fourth dose should have their dose reduced to 0.6 mcg/kg/week. If symptoms do not improve after 3 weeks of the reduced dose, patients may have their dose reduced to 0.3 mcg/kg/week. If symptoms do not improve after 3 weeks of the second dose reduction, the patient should be taken off treatment.

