6.3 Non-hematologic toxicity other than constitutional symptoms

- Subjects who experience a grade 4 non-hematologic toxicity, or subjects who experience grade 2 or higher cardiopulmonary toxicity that is at least possibly-related to SYLATRON should be removed from protocol treatment and should not restart the drug.
- The development of any other SYLATRON related grade 3 non-hematologic toxicity should result in immediate discontinuation of the drug. Following the discontinuation of the drug, patient should be monitored and may restart the drug if following conditions are met:

Subjects who develop grade 3 SYLATRON-related non-hematologic toxicity other than constitutional symptoms should have the drug withheld until the toxicity resolves to grade ≤1. If the toxicity resolves to Grade 1 or better within 3 weeks of discontinuation of SYLATRON, patients may restart therapy at 0.6 mcg/kg/week.

Toxicity that does not resolve within 3 weeks will require the subject to be removed from protocol therapy. If the toxicity recurs at the 0.6 mcg/kg/week dose, the dose should be decreased to 0.3 mcg/kg/week, provided toxicity has decreased to Grades 0-1 within 3 weeks of discontinuation of SYLATRON. Recurrent Grade 3 non-hematologic toxicity following two dose reductions will require the subject to be removed from protocol therapy. No subsequent dose escalations are permitted after dose reduction for non-hematologic toxicity.

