Subjects who develop persistent (≥7 days) grade 2 non-hematologic SYLATRON related toxicities (other than constitutional symptoms and transaminase elevations) that are considered sufficiently medically significant or sufficiently intolerable by patients as to warrant treatment interruption and/or dose reduction should have SYLATRON withheld until the toxicity resolves to grade ≤ 1 . If the toxicity resolves to Grade 1 or better within 3 weeks of discontinuation of SYLATRON, patients may restart therapy at the same dose. Toxicity that does not resolve within 3 weeks will require the subject to be removed from protocol therapy. If the grade 2 toxicity recurs, the SYLATRON dose should be withheld again until the toxicity resolves to grade 1 or better, at which point the dose should be decreased to 0.6 mcg/kg/week, provided toxicity has decreased to Grades 0-1 within 3 weeks of discontinuation of SYLATRON. If the toxicity recurs at the 0.6 mcg/kg/week dose, the dose should be decreased to 0.3 mcg/kg/week, provided toxicity has decreased to Grades 0-1 within 3 weeks of discontinuation of SYLATRON. Recurrent Grade 2 non-hematologic toxicity following two dose reductions will require the subject to be removed from protocol therapy. No subsequent dose escalations are permitted after dose reduction for non-hematologic toxicity.

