6.4 Dose Modification for Hematologic Toxicity

Any subject who has an ANC $<1000/\mu L$ or platelet count $<100,000/\mu L$ should have the test repeated within 1 week (prior to the next dose of SYLATRON). The criteria for dose modification are as follows:

- Absolute neutrophil count (grade 4) <500/μL
- Platelets (grade 3) < 50,000/ μ L

Whenever a subject's blood count(s) drop below the criteria shown above, the SYLATRON will be held until the count(s) recover to Grades 0-1 and the dose will be reduced to 0.6 mcg/kg/week. Toxicity must recover to Grades 0-1 within 3 weeks of discontinuation of SYLATRON in order to allow re-initiation of treatment at the reduced dose. Toxicity that does not resolve within 3 weeks will require the subject to be removed from protocol therapy. Should the toxicity recur at the 0.6 mcg/kg/week dose level, a second dose reduction to 0.3 mcg/kg/week should be performed provided the toxicity has decreased to Grades 0-1 within 3 weeks of discontinuation of SYLATRON. If there is again recurrence of hematologic toxicity meeting the above requirements for dose reduction (i.e., following the second dose reduction) treatment with SYLATRON will be discontinued permanently. No subsequent dose escalations will be permitted after dose reduction for hematologic toxicity.

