8.1.1 Agent Ordering

Study Agent/s may be requested by the Principal Investigator (or their authorized designees) at each participating institution. All regulatory document requirements, as described by the PBTC, must be current and up to date prior to requesting study agents.

8.1.2 Drug Requests:

Drug request forms and instructions can be found on the PBTC-039 protocol and resources webpage. Peginterferon alfa-2b (SYLATRON) drug requests should be sent to Almac Clinical Services.

[name] Project Manager - Distribution Almac Clinical Services

8.1.3 Product description:

PEG₁₂₀₀₀-IFN Powder is a white to off-white lyophilized powder supplied in 2-ml vials for subcutaneous use.

8.1.4 Solution preparation:

Each vial of SYLATRON contains 296 mcg of PEGINTERFERON ALFA-2B with dibasic sodium phosphate, monobasic sodium phosphate, sucrose and polysorbate 80. Following reconstitution with 0.7 mL of Sterile Water for Injection USP (or equivalent), each 0.5 mL contains 200 mcg PEGINTERFERON ALFA-2B. No more than 0.5 mL should be taken from any single vial. This allows for an overfill volume to compensate for residual volume in the vial and syringe/needle hub during withdrawal, as well as for volume displacement by the excipients during reconstitution. The clear, colorless solution has a pH of 6.5 to 7.1, is iso-osmotic, and unless otherwise specified, is intended to be used directly from the vial for SQ injection.

8.1.5 Storage requirements:

SYLATRON should be stored at 25°C, excursions permitted to 15-30°C. Do not freeze. Keep away from heat. After reconstitution with supplied diluent, the solution should be used immediately, but may be stored up to 24 hours at 2 to 8°C. The reconstituted solution contains no preservative, is clear and colorless. Upon completion of the study, all remaining study drug will be destroyed and disposed of pursuant to the ICH/GCP Guidelines and Institutional policies.

8.1.6 Stability:

The reconstituted solution is stable for 24 hours when stored refrigerated between 2-8°C (36-46°F). However, it is recommended that the solution be used within 3 hours after mixing.

8.1.7 Route of administration:

SYLATRON (PEGINTERFERON ALFA-2B) will be administered subcutaneously. The following syringes and needles are recommended: B-D disposable syringes (Tuberculin syringes), B-D Number 30963; Needle gauge: 27; Length: 1/2 inches (13 mm). Dosing instructions are provided in Appendix C

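### Toxicity reductions to 0.6 and 0.3 mcg/kg/week fall below the plan's stated 0.05 mL minimum injection for patients under 33.3 kg and 66.7 kg, and the text does not reconcile the two

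*Combined protocol and SAP*

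**What the plan says.** Section 3.1.10 requires a body weight of at least 20 kg and gives the reason: "since the minimum injection volume of SYLATRON is 0.05 ml, 20 mcg, SQ as suggested by Merck". Section 6 carries the weight limit into treatment: "If patients drop below 20 kg during SYLATRON treatment, they can have SYLATRON held for up to 3 weeks". Drug restarts only once weight is back to 20 kg, and this may happen twice before removal.

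The starting dose is 1 mcg/kg/week for everyone (Section 5.1). The reductions carry no weight condition:

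- Section 6.1, constitutional symptoms: patients "should have their dose reduced to 0.6 mcg/kg/week", with a possible second step to 0.3.
- Section 6.3, grade 3 non-hematologic toxicity: "patients may restart therapy at 0.6 mcg/kg/week", then 0.3 on recurrence.
- Section 6.3, recurrent grade 2 toxicity: drug is withheld until recovery, "at which point the dose should be decreased to 0.6 mcg/kg/week", then 0.3.
- Section 6.4, hematologic toxicity: 0.6, and on recurrence "a second dose reduction to 0.3 mcg/kg/week should be performed".

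There is one concentration. Section 8.1.4 states that after reconstitution "each 0.5 mL contains 200 mcg PEGINTERFERON ALFA-2B", and Appendix C lists the same strength. The Appendix C formula accepts any dose per kilogram, but its chart covers 1 mcg/kg only, and its smallest volume is 0.05 mL. Patients or parents prepare and give the injections at home (Section 5.1, Appendix B).

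**The concern.** The plan describes 0.05 mL as the smallest SYLATRON injection and excludes children under 20 kg on that ground, yet it orders smaller injections for many patients who need a dose reduction. The contrast is sharpest around 20 kg. A child who slips to 19 kg on full dose would draw 0.0475 mL and falls under the hold rule. A 20 kg child on the second reduction would draw 0.015 mL, and the plan says nothing about it.

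A site has to choose. If it follows the formula, a parent measures a volume below the stated minimum with no instruction on how to do so. If it applies the minimum, the reduction is partly or wholly lost in a patient who already has toxicity. Under Section 6.3, toxicity that recurs after two reductions ends protocol therapy, so a 20 kg child could come off drug after two reductions that never lowered the dose. If sites choose differently, the planned tabulation of dose reductions (Section 13.3, Analysis Plan) would mix real reductions with nominal ones.

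**Working it through.** **Inputs.** Minimum injection 0.05 mL, 20 mcg (Section 3.1.10). Concentration 200 mcg / 0.5 mL = 400 mcg/mL (Section 8.1.4, Appendix C). Dose levels 1, 0.6 and 0.3 mcg/kg/week (Sections 5.1, 6.1, 6.3, 6.4).

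**Formula (Appendix C).** Volume in mL = weight × dose per kg / 400. The weight at which a dose level just reaches the minimum is 0.05 × 400 / dose = 20 / dose.

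**The plan's own figures.** At 1 mcg/kg the break-even weight is 20 / 1 = 20 kg, which is the stated limit. The worked example, 60 kg at 1 mcg/kg, gives 60 / 400 = 0.15 mL, as printed.

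**Break-even weights at the reduced levels.** 20 / 0.6 = 33.3 kg and 20 / 0.3 = 66.7 kg.

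**If the formula is followed:**

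| Weight | 0.6 mcg/kg | 0.3 mcg/kg |
|---|---|---|
| 20 kg | 12 mcg, 0.030 mL | 6 mcg, 0.015 mL |
| 28 kg | 16.8 mcg, 0.042 mL | 8.4 mcg, 0.021 mL |
| 32 kg | 19.2 mcg, 0.048 mL | 9.6 mcg, 0.024 mL |
| 40 kg | 24 mcg, 0.060 mL | 12 mcg, 0.030 mL |
| 64 kg | 38.4 mcg, 0.096 mL | 19.2 mcg, 0.048 mL |
| 68 kg | 40.8 mcg, 0.102 mL | 20.4 mcg, 0.051 mL |

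Of the 26 weight rows in the Appendix C chart, 4 (20 to 32 kg) fall below 0.05 mL at 0.6 and 12 (20 to 64 kg) at 0.3. These counts locate chart cells; they are not shares of patients.

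**If the minimum is applied instead.** The lowest weekly dose is 20 / weight:

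- 20 kg: 1.0 mcg/kg, so no reduction. This is 1.0 / 0.6 = 1.67 times the first reduced dose and 1.0 / 0.3 = 3.33 times the second.
- 28 kg: 20 / 28 = 0.71 mcg/kg, against 0.6 ordered.
- 40 kg: 20 / 40 = 0.5 mcg/kg, which is 1.67 times the 0.3 level.
- 60 kg: 20 / 60 = 0.33 mcg/kg, close to the 0.3 level.

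Below 33.3 kg both reduced doses come to less than 20 mcg, so both would become 20 mcg and the second step would change nothing.

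**Near the break-even weights the gap is trivial.** At 32 kg on 0.6 and at 64 kg on 0.3 the shortfall is 20 − 19.2 = 0.8 mcg, or 4% of the minimum.

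**The case against.** The strongest reply is that nothing needs reconciling. The 0.05 mL figure appears once, as the reason for an entry weight, and is attributed to a supplier suggestion that the documents do not reproduce. Section 6 carries forward a body-weight rule, not a volume rule. The statement in Section 3.1, "All subjects must meet the following inclusion and exclusion criteria. No exceptions will be given", governs eligibility and does not turn the minimum into an on-treatment dosing floor. The reductions are explicit and the formula takes a variable dose, so the protocol already yields a volume at every level. Giving 20 mcg to a child ordered to 12 or 6 mcg would contradict Section 6.

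Much of this stands. Following the ordered reduction and the formula is the more natural reading, and the loss of the reduction arises only if a site departs from it. What does not fall away is that the minimum is worded as a property of the product, and its weight limit still operates after entry. If smaller volumes are acceptable, the on-treatment weight rule has lost its stated reason. If they are not, the reductions cannot be delivered as written.

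A reader might also infer a large measuring error at volumes such as 0.015 mL, by assuming doses are rounded to the chart's 0.01 mL steps. The documents do not support that. The steps follow from the 4 kg row spacing, no section orders rounding to them, and Section 8.1.7 recommends tuberculin syringes without giving graduations. In-between volumes occur at full dose too: 22 kg gives 22 / 400 = 0.055 mL.

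**Conclusion.** The concern holds as an unreconciled dosing instruction. By the plan's own formula, the reduced doses fall below the stated minimum under 33.3 kg (0.6 mcg/kg) and under 66.7 kg (0.3 mcg/kg), and no text says which governs. The thresholds are exact given the single 400 mcg/mL strength.

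A reader might infer that the reductions are undeliverable, or that children are being denied them. The documents do not show either: the supplier's suggestion is not reproduced, so whether it covers reduced doses is unknown, and the multiples of 1.67 and 3.33 at 20 kg apply only where a site puts the minimum first. Nor is this confined to small children, since the trial enrolls to age 25 and the second threshold is 66.7 kg.

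The number of patients affected cannot be computed. No weight distribution is given, and the minimum is stated for SYLATRON only, not for the product it replaced. Reductions are foreseeable but not frequent: in the pediatric Phase I study cited in Section 2.2.3, in a different disease, there was one dose-limiting toxicity among 12 patients at this dose, and one other patient needed a reduction.

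This is a minor dosing-safety correction. Sample size, type I error and power are unaffected.

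**What to change.** 1. Add 0.6 and 0.3 mcg/kg columns to the Appendix C chart and flag volumes below 0.05 mL: rows 20 to 32 kg at 0.6, and rows 20 to 64 kg at 0.3.
2. State in Section 6 that the 0.05 mL minimum sets the entry and on-treatment weight limit at the 1 mcg/kg dose, and that it must not cancel or round up a toxicity reduction. Give a measuring method for smaller volumes, confirmed with the supplier.
3. Only if the supplier does not allow smaller volumes, replace the second sentence of that rule with the weights below which each reduced level is unavailable. If 0.05 mL is upheld, these are 33.3 kg for 0.6 and 66.7 kg for 0.3. A patient who needs an unavailable level would stop drug under the toxicity reason in Section 5.3.2 and be followed for progression under Section 5.4.2.

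The cost of the first two items is two chart columns, one short rule and one supplier confirmation; every dose level is kept. The third item costs more. Patients under 33.3 kg would lose both reduced levels, and those from 33.3 kg to under 66.7 kg would lose the second. It can also reach the Stratum 1 endpoint: Section 13.3 bases the design on completing 9 courses without an event, and Section 13.4.1 counts as failures patients who are removed from treatment and not evaluated for the primary outcome. Continued follow-up lessens this but does not settle it, so the plan should acknowledge the effect if this route is taken.
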